## 5. Methods and Study Design

This is a randomized controlled trial designed to test efficacy of 4Q-TAP against TEA (routine of care) on quality of recovery 48 hours after CRS-HIPEC surgery. All patients will be enrolled at MD Anderson Cancer Center.

### **A. Setting and Population**

#### *Inclusion criteria:*

1. Written informed consent;
2. 18 years old or older;
3. American Society of Anesthesiologists physical status (ASA) 1-3;
4. Scheduled surgery: open elective CRS-HIPEC;
5. Able to complete the QoR 15 questionnaire;
6. Patients scheduled to receive intraoperative chemotherapy;

#### *Exclusion criteria:*

1. Contraindications to epidural analgesia due to thrombocytopenia (platelet count: <100,000 cell/dL), coagulopathy (International Normalized Ratio > 1.5, PT>16.5 seconds or aPTT > 35.9 seconds);
2. Bupivacaine or liposomal bupivacaine sensitive or known allergy;
3. Pregnancy or breastfeeding patients;
4. Patients with recent (within 60 days preoperatively) history severe hepatic disease (defined as liver injury with encephalopathy plus impaired synthetic liver function (i.e. > 1.5))
5. Patients with recent (within 15 days preoperatively) history deteriorate kidney function (creatinine serum concentrations > 2.5 mg/dL or eGFR < 30 mL/kg/min);

### **B. Withdrawal of Patients**

Patients may withdraw from the study at any time, with or without reason and without prejudice to further treatment. In all cases of withdrawal, the reason(s) for withdrawal (if given) will be recorded upon study termination.

In addition, the investigator may withdraw the patient due to any of the following situations:

- adverse event
- any other reason determined by the investigator to be in the best interest of the patient.

Patients withdrawn due to an adverse event should be followed until the event has been resolved or is stable, if at all possible.

## **B. Interventions**

Patients will be randomized 1:1 on the morning of surgery to one of the following 2 interventions:

**TEAgroup:** Patients in this group will be treated as standard of care. An epidural catheter will be placed before induction of anesthesia by an anesthesiologist. The catheter will be placed between the thoracic vertebral spaces 8 and 12 according to routine care. A bolus or infusion of local anesthetic solution with or without the addition opioids will be given before surgical incision according to anesthesia provider's clinical judgment. If deemed appropriate, a pre-incision epidural bolus of hydromorphone (300-800 micrograms) may be administered according to the anesthesia provider's clinical judgment.

**4Q-TAP block group:** Patients in this group will have an ultrasound guided 4Q-TAP block. A maximum of 80 cc of a solution consisting of 30 mg of bupivacaine HCl in 10 cc of PFNS and 65 mg of liposomal bupivacaine in 10 cc of PFNS will be injected before surgical incision in each of the four quadrants.

## **C. Protocol and procedures**

Patients will be screened from surgical and preoperative anesthesia clinic schedules and visits. The study team including the PI, Co-PIs or collaborators will approach patients for consenting only after confirmation of inclusion and exclusion criteria. After consenting, **patients will be free to withdraw from study at any time.**

After enrolling to the study and prior randomization, all data pertinent to the study and the QoR 15 will be obtained by the research personnel involved in the study. After randomization, all patients will have surgery under general anesthesia according routine care. All patients will receive intra- and postoperative multimodal analgesia according to the standard of care and judgment of the attending anesthesiologists. Before surgery, p.o. celecoxib, tramadol extended release and/or pregabalin will be administered according to clinical judgment. Intraoperative infusions of propofol, dexmedetomidine and ketamine will be permitted per standard of care. Intravenous infusion of lidocaine will not be permitted at any time. Intravenous fentanyl, sufentanil or hydromorphone will be administered according to clinical judgment of the attending anesthesiologist. Prophylactic antibiotics will be given per surgical routine care. Medications for prophylaxis of nausea and vomiting (dexamethasone 8-10 mg, ondasetron 4-8 mg and/or aprepitant 80-125 mg) will be given according to the judgment of the attending anesthesiologists.

Upon arrival to the postoperative anesthesia care unit or intensive care unit, postoperative analgesia will consist of the administration of boluses of hydromorphone or fentanyl to achieve a pain score < 4 (on a 0-10 NRS). If needed, patients will receive intravenous patient-controlled analgesia with hydromorphone or fentanyl. Once patients can tolerate p.o. medications, they will transition to oral

analgesics according to standard of care. Patients in the epidural group will have the catheter removed per routine care.

Patients will be encouraged out of bed mobilization per standard of care. Foley catheter will be removed 48 hours after surgery if clinically indicated.

#### ***D. Data collection and measurements***

**Preoperative data:** Demographic data to be obtained includes height (cm), weight (kg), age (yr), gender, (ASA) physical status, and self-declared ethnicity. Patients will be questioned for social history (tobacco) and medical history to calculate Charlson comorbidity index score. QoR 15 will be obtained before surgery. Pain meds (type, dose and frequency)

The following **intraoperative data** will be obtained from electronic medical records: surgery and anesthesia time, surgery type and extent of resection, intraoperative chemotherapy (type and dose), highest temperature, intraoperative anesthetic and opioid consumption. Blood loss, fluid therapy and urinary output will also be collected at the end of surgical procedure.

The following **postoperative data** will be obtained from electronic medical records: Postoperative opioid consumption, breakthrough pain medication requirements and oxygen requirements in PACU and in nursing floor (first 48 hours postoperatively). QoR score and pain scores will be obtained on postoperative day 1, 2, 3, 5, 7, 10( $\pm$ 1) and 30( $\pm$ 2) days if the patient is still admitted to the hospital. Nausea and vomiting, requirement of antiemetics, pruritus, requirement of antihistaminic medications and requirement of naloxone in PACU and first and second postoperative morning after surgery will be collected. Ambulation time, flatus and bowel movements (first time), constipation, length of stay will be obtained. Incentive spirometry will be measured on postoperative day 1 and 2. Postoperative complications (Clavien-Dindo scale during hospital admission) and perioperative morbidity scores (POMS day 7) will be obtained from medical records and 30 days after surgery. Preoperative and postoperative routine laboratory data results will also be collected from electronic medical records.

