#### *4-quadrant TAP block*

**To enhance the analgesic efficacy of the traditional TAP block**, several authors have added a subcostal approach to provide analgesia to the upper half of the abdomen. In a cadaveric study of the four-quadrant TAP block (4QTAP), dermatomes T8-L1 were adequately covered with the solution of local anesthetic. Therefore, it was originally hypothesized that the 4QTAP block may be more beneficial in major abdominal surgery compared to the traditional TAP approach alone. In a prospective study of 124 patients, the surgical incision for abdominal surgery was within the dermatomal limits of the 4QTAP in 70% of patients. In a later study by Niraj et al, the authors demonstrated that 4QTAP with levobupivacaine resulted in similar pain scores and tramadol consumption when compared to epidural analgesia for laparoscopic colorectal surgery.

**The 4QTAP block may provide some advantages over epidural analgesia** as TAP blocks are associated with more stable hemodynamics and less use of vasopressor and intravenous fluids during and after surgery. In addition, 4QTAP blocks are not associated with postoperative urine retention neither the risk of epidural hematoma or infections. Lastly, the use of 4QTAP blocks can reduce the use of resources and personnel because there is no need for frequent monitoring of the epidural catheter and infusions pumps.

With the increased safety of ultrasound guided needle placement and 'real-time' visualization through dynamic scanning, **serious complications are rare** with the 4QTAP block. Needle puncture thru the peritoneum causing bowel or diaphragm perforation is unlikely, but is still a possibility. The abundance of structures in the peritoneal cavity makes the viewing of the needle in plane at all times during needle advancement of utmost importance. Lacerations of the liver have been reported during placement of right-sided TAP blocks. Abdominal wall hematoma, vascular injury, local anesthetic toxicity and are also potential, but rare complications.

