### **Adverse Event Definition**

An adverse event is any symptom, sign, illness, or experience which develops or worsens during the course of the study, whether or not the event is considered related to study drug. **Adverse events (AEs) related to the study interventions** will be recorded within the first 48 hours after the end of surgery. AEs related to the study will include postoperative hypotension needed pharmacological intervention including fluid resuscitation or temporary holding or discontinuation of epidural infusions, failed block (defined as patchy block or unilateral block needing pharmacological interventions or catheter removal), epidural space infection or abscess and epidural hemathoma.

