### **Serious Adverse Event**

A serious adverse event is defined as any adverse medical experience that results in any of the following outcomes:

- death;
- is life-threatening;
- requires inpatient hospitalization or prolongation of existing hospitalization;
- results in persistent or significant disability/incapacity;
- is a congenital anomaly/birth defect; or
- requires medical or surgical intervention to prevent permanent impairment or damage.

**Opioid-related adverse** (i.e. respiratory depression, pruritus, sedation, delirium) within the first 48 hours after the end of surgery.

[figure not shown]
**Postoperative complications** will be recorded using Clavien-Dindo scale and POMS.

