**Table 1 Study Event Schedule**

	Baseline (within 60 days prior to surgery)	Day of surgical Procedure	First 48 hours after surgery	Procedures until Discharge	Procedures After Discharge
Informed Consent	X a				
Inclusion / Exclusion Criteria Assessment	X				
Demographics/ Medical History	X				

Randomization and Intent to Treat		X b			
Vital Signs	X c	X c			
Physical Examination	X				
Laboratory Tests	X d				
Data collection	X e	X e	QoR15, pain scores, opioid consumption,	QoR15, pain scores, opioid consumption, LOS	QoR15, pain scores, opioid consumption,
Adverse Events		X f	ORADE, AE, SAE, complications (Clavien-Dindo)		

a After confirmation of eligibility and 30 days after surgery.

b After confirmation of eligibility and before surgery.

c Height, weight, systolic/diastolic blood pressure, heart rate, and respiratory rate (height and weight will only be measured at baseline)

c Data will be collected from the patients standard of care lab tests. These typically include creatinine, platelet and white blood cells count, and hemoglobin and hematocrit

d Complete blood counts, routine electrolyte determinations and renal function laboratory tests collected

e ORADE: opioid related adverse effects, AE: adverse events, SAE: serious adverse events, QoR: quality of recovery, LOS: length of stay

f During surgery, at PACU discharge and POD1 and 2.

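### Aims 4 and 5 compare 48-hour event rates, but the readable text schedules no assessment of sedation, respiratory depression, delirium or hypotension, so detection may differ by arm

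*Combined protocol and SAP*

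**What the plan says.** Section 3 (Study Aims) hypothesises lower 48-hour incidence with 4Q-TAP for intervention-related events, including hypotension (Aim 4), and for opioid-related events (Aim 5). The Safety paragraph under Secondary Outcomes Analyses compares event rates by Fisher's exact test.

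**Window.** Adverse Event Definition says intervention-related events "will be recorded within the first 48 hours after the end of surgery". The opioid-related events are described as "i.e. respiratory depression, pruritus, sedation, delirium) within the first 48 hours after the end of surgery"; a figure that is not shown follows that line.

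**Schedule.** In Table 1 (Study Event Schedule) the adverse-event row is not split by arm and has "ORADE, AE, SAE, complications (Clavien-Dindo" in the 48-hour column. Footnote f gives the times "During surgery, at PACU discharge and POD1 and 2". The vital-sign row covers "systolic/diastolic blood pressure, heart rate, and respiratory rate (height and weight will only be measured at baseline" and is marked at baseline and on the day of surgery only.

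**Data collection.** Section 5.D draws postoperative data from electronic medical records. Its timed list (nausea and vomiting, antiemetics, pruritus, antihistamines, naloxone) ends "requirement of naloxone in PACU and first and second postoperative morning after surgery will be collected". Oxygen requirement is collected over the first 48 hours. Sedation, respiratory depression, delirium and hypotension are not listed.

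**Hypotension.** The counted event is "postoperative hypotension needed pharmacological intervention including fluid resuscitation or temporary holding or discontinuation of epidural infusions".

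**Care by arm.** Section 4.B says TEA calls for active postoperative management. Section 4.C says of the 4Q-TAP block that "there is no need for frequent monitoring of the epidural catheter and infusions pumps".

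**The concern.** A between-arm comparison of event rates is fair only if an event has about the same chance of being recorded in each arm. The readable text fixes when events are recorded, but not how three of Aim 5's four named events (sedation, respiratory depression, delirium) or Aim 4's hypotension are looked for between those points. Recording then rests mainly on routine charting. The title calls the study single-blinded without saying who is blinded, and staff running an epidural infusion know the arm in any case. If the more active management under TEA brings more observation, more events may be charted there, which is the direction that both aims hypothesise. Fisher's test cannot separate fewer events from fewer observed events.

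Two further points affect the same comparisons. The timed items can stop before the 48-hour window closes. And hypotension has a criterion that a 4Q-TAP patient cannot meet.

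**Working it through.** The documents give no incidence or detection rate for these events, so there is no planned figure to reproduce. The check sets the sections side by side and then shows ranges under stated assumptions.

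**1. How each event is captured in the readable text**

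| Event | Timed item in 5.D | Vital signs after day of surgery | Other capture |
|---|---|---|---|
| Pruritus | Yes, PACU and two mornings | n/a | Antihistamine use |
| Respiratory depression | No | None marked | Naloxone and oxygen use (indirect); Table 1 adverse-event row |
| Sedation | No | n/a | Table 1 adverse-event row |
| Delirium | No | n/a | Table 1 adverse-event row |
| Hypotension | No | None marked | Table 1 adverse-event row; counted only if acted on |

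The adverse-event row is common to both arms. It states what is recorded and when, not the method or the frequency of observation between those points.

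**2. Coverage of the window by the timed items**

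Assumptions: surgery ends between 14:00 and 20:00, and the POD 2 morning check is at 08:00.
- End at 14:00: the check falls at 42 h, leaving 48 − 42 = 6 h (6/48 = 12.5%).
- End at 20:00: the check falls at 36 h, leaving 48 − 36 = 12 h (12/48 = 25%).

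This applies equally to both arms. It is incomplete capture, not differential bias.

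**3. What unequal detection would do**

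Inputs: 80 per arm (synopsis) and Fisher's exact test (Safety paragraph). Assumptions: two-sided 0.05, the same true incidence p in both arms, all events detected under TEA, and a fraction r detected under 4Q-TAP. The recorded rates are then p and p × r. For p = 20% and r = 0.7 that is 80 × 0.20 = 16 expected recorded events against 80 × 0.14 = 11.2.

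The chance of a spurious result favouring 4Q-TAP is the sum of Bin(i; 80, p) × Bin(j; 80, pr) over all pairs with i > j and Fisher p ≤ 0.05:

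| True incidence | r = 1.0 | 0.9 | 0.8 | 0.7 | 0.5 |
|---|---|---|---|---|---|
| 10% | 1.4% | 2.3% | 3.8% | 6.0% | 14.2% |
| 20% | 1.6% | 3.4% | 6.7% | 12.4% | 34.8% |
| 30% | 1.7% | 4.3% | 10.0% | 20.3% | 56.3% |
| 40% | 1.6% | 5.4% | 14.4% | 30.5% | 74.5% |

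With 70 per arm (half of the 140 in the sample-size table) the 20% row is 1.6, 3.2, 6.1, 11.1 and 30.4%. A 10% gap in detection matters little; a gap of 30% or more on a common event matters a good deal.

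**4. Hypotension**

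The definition has two routes: drug or fluid treatment, which either arm can meet, and holding or stopping an epidural infusion, which only TEA patients can meet. An episode handled only by the second route adds to the TEA count and has no counterpart under 4Q-TAP.

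**The case against.** A reader might infer that the trial has no common schedule for these events. The documents do not support that: the adverse-event row is shared, footnote f gives common times (it is attached to the day-of-surgery cell, but its text runs to POD 2), the 48-hour window is the same for both arms, and the General paragraph under Adverse Events monitors all events to the end of the study.

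Nor does the protocol say that TEA patients will be checked more often for these events. The 4Q-TAP sentence is about catheters and pumps. No observation frequency by arm is given, and intravenous patient-controlled opioids are allowed if needed without restriction by arm. That TEA events will be over-detected is therefore inference; that they may be is as far as the text goes.

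Hypotension counts only when acted on, so it depends less on how often pressure is read. The figure not shown after the opioid-related event line may hold definitions or methods, so these cannot be called absent. The early end of the timed items affects both arms and is no evidence of bias. Only secondary aims are involved; the QoR-15 primary comparison is untouched.

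All of this stands and limits the point. It does not close the gap: a shared recording time does not show how an event between contacts comes to be noticed, and the readable text has nothing to make that equal.

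**Conclusion.** The point holds in a limited form. The 48-hour window and recording points are common, but in the readable text sedation, respiratory depression, delirium and hypotension have no scheduled assessment and rest largely on routine charting. Detection may be higher under TEA, in the direction of the Aim 4 and 5 hypotheses.

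The size is unknown. The table in the working shows what a gap would do under its assumptions, not what is expected. A reader might infer that detection is halved under 4Q-TAP, for example by supposing a 2-hour event checked every 4 hours (2/4 = 50%) against every 2 hours (2/2 = 100%). The documents give neither event durations nor check intervals, so they do not support that figure.

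Two smaller points rest on the text itself. Capture of the timed items can end before 48 hours in both arms; the 6 to 12 h shortfall assumes the clock times used above. And the hypotension definition includes a route open only to TEA patients.

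**What to change.** Amend section 5.D, Adverse Event Definition and Table 1:

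- Take naloxone, antihistamine and antiemetic use cumulatively from the medication record through 48 hours in both arms.
- Extend the vital-sign row to 48 hours, using routine flowsheet data.
- Assess sedation and delirium with the same brief standard tool in both arms at the POD 1 and POD 2 contacts already made for the QoR-15 and pain scores.
- For the between-arm hypotension comparison, count hypotension needing drug or fluid treatment, which either arm can meet. Report holding or stopping of an epidural infusion separately.
- Keep all clinically charted events in the safety tables, and do not discard readings prompted by the epidural, since that would remove real events.

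The cost is protocol wording, some extra record extraction and a few minutes at two existing contacts; treatment does not change. A limit remains: routine flowsheet readings need not be equally frequent in the two arms, and brief episodes of sedation or delirium between contacts still depend on charting. The change reduces the room for unequal detection but does not remove it.

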#### ***Duration of Patient Participation***

Patients that consent to the optional MDASI questionnaires will participate until the POMS data has been completed on postoperative day 30.

#### ***E. Outcomes definitions***

**Quality of Recovery** will be measured using the QoR-15 scale. The QoR scale is a validated scoring system that allows for the quantification of a patient's early postoperative health status.

**Pain Intensity at rest and cough** will be measure using a VNRS (0 = no pain - 10 = worst pain ever). Data will be reported as time-weighted pain scores from discharge from the PACU until 48 hours after the end of surgery.

**Opioid Consumption** will be reported as morphine equivalents required during the 48 hours after the end of surgery.

**Length of stay** will be calculated from day of surgery to date of hospital discharge.

### **Adverse Event Definition**

An adverse event is any symptom, sign, illness, or experience which develops or worsens during the course of the study, whether or not the event is considered related to study drug. **Adverse events (AEs) related to the study interventions** will be recorded within the first 48 hours after the end of surgery. AEs related to the study will include postoperative hypotension needed pharmacological intervention including fluid resuscitation or temporary holding or discontinuation of epidural infusions, failed block (defined as patchy block or unilateral block needing pharmacological interventions or catheter removal), epidural space infection or abscess and epidural hemathoma.

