## Adverse Events

### General

All adverse events (AE) and serious adverse events (SAE) will be monitored from the time of procedure through end of the study.

An AE is defined as any undesirable clinical occurrence in a patient whether or not it is considered to be device related. In addition, the definition of AE applies to any event with an onset post study procedure or to any underlying diseases, present at baseline, that exacerbate in severity post study procedure. Therefore, an underlying disease that was present at the time of enrollment is not reported as an AE, but any increase in the severity of the underlying disease is to be reported as an AE. All reported AEs must be recorded in the database. A description of the event, including the start date, resolution date, action taken, and the outcome should be provided, along with the Investigator's assessment of the relationship between the AE, the study treatment and the study procedure. This protocol will use common terminology criteria for adverse events (CTCAE) version 4.0. For the AEs not characterized in the CTACE, the following definitions for rating severity of AEs will be used:

Mild: Awareness of signs or symptoms, but easily tolerated; are of minor irritant type; causing no loss of time from normal activities;

- symptoms would not require medication or a medical evaluation;  
signs or symptoms are transient.
- Moderate: Interferes with the patient's usual activity and/or requires symptomatic treatment.
- Severe: Symptom(s) causing severe discomfort and significant impact of the patient's usual activity and requires treatment.

A serious adverse event (SAE) is defined as an event which leads to:

- Death due to any cause
- Life-threatening condition
- Results in persistent or significant disability/incapacity
- Requires in-patient hospitalization or prolonged hospitalization
- Necessitates an intervention to prevent a permanent impairment of a body function or permanent damage to a body structure
- Results in congenital abnormality

All SAE's will be reported.

***Device-Related Adverse Event:*** Not applicable

***Procedure-Related Adverse Event:*** an adverse event is considered to be procedure-related when, in the judgment of the Investigator; it is reasonable to believe that the event is associated with the assigned study procedure. Other products, surgical techniques, or medications required specifically for the procedure are likely to have contributed to the occurrence of the event.

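### The recording window for intervention-related adverse events opens at the end of surgery, after both blocks have been delivered, and conflicts with two earlier start points elsewhere in the protocol

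*Combined protocol and SAP*

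**What the plan says.** Under E. Outcomes definitions, the Adverse Event Definition says that events related to the study interventions "will be recorded within the first 48 hours after the end of surgery". It continues: "AEs related to the study will include postoperative hypotension needed pharmacological intervention". The rest of its list is failed block, epidural infection or abscess, and epidural hematoma. Secondary Aim 4 compares this kind of event between arms, gives postoperative hypotension and failed block as its examples, and hypothesizes a lower incidence with 4Q-TAP.

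B. Interventions sets the timing of both techniques. For TEA, "An epidural catheter will be placed before induction of anesthesia by an anesthesiologist", and "A bolus or infusion of local anesthetic solution with or without the addition opioids will be given before surgical incision". For 4Q-TAP, the solution "will be injected before surgical incision in each of the four quadrants".

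Two other places set a start for adverse event collection:

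- Table 1 Study Event Schedule, Adverse Events row, day-of-surgery column, footnote f: "During surgery, at PACU discharge and POD1 and 2".
- Adverse Events, General: all AEs and SAEs "will be monitored from the time of procedure through end of the study".

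The Background section on the 4-quadrant TAP block lists the harms of that technique: bowel or diaphragm perforation, liver laceration and abdominal wall hematoma, and it adds that "vascular injury, local anesthetic toxicity and are also potential, but rare complications".

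**The concern.** Aim 4 is the secondary aim that compares block-related harm between the arms. A window that opens when the operation ends starts after the needle work, the first epidural dosing and the whole TAP injection. The period in which acute placement complications would be expected is therefore outside the definition of the outcome meant to compare them.

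The event list is also uneven. It names infection, abscess and hematoma of the epidural space, but none of the TAP harms that the Background acknowledges. Because Aim 4 expects fewer events with 4Q-TAP, a favorable result would be open to the criticism that TAP-specific events were neither named nor inside the window.

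Finally, there are three start points and no statement of which governs Aim 4. Two analysts working from the same database could count different events.

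**Working it through.** No arithmetic applies. The check sets the timeline of delivery against the three windows.

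**Order of events (B. Interventions).** Epidural catheter placement, then induction. Epidural dosing and TAP injection both come before incision. Surgery and its end follow.

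**Where each window opens**

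| Source | Opens | Placement covered? | Intraoperative period covered? |
|---|---|---|---|
| Adverse Event Definition | End of surgery | No | No |
| Table 1, footnote f | During surgery | Not clearly: the catheter precedes induction | Yes |
| Adverse Events, General | Time of procedure | Depends on whether procedure means the block or the operation | Yes |

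**Which events fall outside Aim 4 as defined**

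1. A placement event that starts and resolves before the end of surgery is outside the Adverse Event Definition. Examples are a vascular puncture managed at the time, or local anesthetic toxicity soon after injection.
2. A placement harm that first appears, or is still present, after surgery can fall inside it. Failed block, epidural hematoma and epidural infection are named and count if they appear within 48 hours. A liver laceration or abdominal wall hematoma that shows itself postoperatively is inside the time window, although the list does not name it.
3. Intraoperative hypotension is outside it twice over: by the window, and because the component is labelled postoperative.

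**Which events are picked up elsewhere**

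1. The Synopsis defines the primary safety endpoint as all reported adverse events.
2. The general section asks for every reported AE to be entered with its relationship to study treatment and procedure, and defines a procedure-related class.
3. The list of events not treated as AEs exempts blood pressure changes only when they need no treatment, which implies that treated changes are reportable.
4. The Safety text under Secondary Outcomes Analyses tabulates all, procedure-related and serious events and compares arms by Fisher's exact test.

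**What stays open.** Nothing says whether Aim 4 is analyzed on the set in the Adverse Event Definition or on the procedure-related set in the safety tables. The intraoperative items in D. Data collection and measurements include fluids, blood loss and opioids, but not vasopressor use or block complications. Capture of these events therefore relies on general AE reporting.

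**The case against.** The strongest reply is that the trial does collect these events. A reader might infer from the definition that Aim 4 is the plan's only safety comparison and that placement harms disappear from the trial. The documents do not support that. The named safety endpoint is all reported adverse events, collection during surgery is scheduled, and procedure-related events are compared by arm in everyone who received any part of the intended treatment. This part of the objection stands, and it limits the point to Aim 4 and to the conflict between sections.

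A second reply is that the wording could be read as setting only when recording closes, which would agree with footnote f. The reading is possible, but a start at the end of surgery is the more natural one. That both readings are available is itself a reason to amend. Likewise, the event list is introduced as what will be included, so it may not be exhaustive; but it does not say so.

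A third reply concerns hypotension. A reader might infer that Aim 4 is wrong to omit intraoperative hypotension, since the Background credits TAP blocks with steadier hemodynamics in the operating room as well as afterwards and counts perioperative hypotension against TEA. But the aim, its hypothesis and the outcome definition all say postoperative, so this looks like a deliberate scope. Intraoperative drugs and epidural dosing are also left to clinical judgment, which makes attribution to the block uncertain. This reply stands: the omission is a scope choice, not an error.

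**Conclusion.** The point holds as a conflict between sections with a definite consequence for one secondary outcome. Followed literally, the Adverse Event Definition leaves out of Aim 4 the block-placement events that begin and end before surgery is over, and it names epidural-specific but no TAP-specific harms. Those events may then appear only in the general safety tables.

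The size cannot be put in numbers. The documents give no placement-complication rate, no rate of treated intraoperative hypotension in either arm and no operating time; of serious TAP complications they say only that they are rare. Any count of missed events would be guesswork, and a count for the TEA arm alone would say nothing about the difference between arms. The net direction is also unknown: leaving out TAP placement events would favor 4Q-TAP, and leaving out epidural placement events would favor TEA.

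The conclusion assumes that the window starts at the end of surgery, as the sentence most naturally reads. It does not affect the primary QoR-15 analysis. It is worth correcting because the remedy is small and the comparison concerns harm from the two techniques under test.

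**What to change.** Reconcile the Adverse Event Definition, Table 1 (footnote f) and the general Adverse Events section so that one start governs Aim 4: the start of epidural catheter placement or of TAP needle insertion. State whether procedure in the general section means the block or the operation.

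Count placement complications in both arms, and add to the list the TAP harms that the Background already names. Report the intraoperative and postoperative periods separately, so that the postoperative hypotension component keeps its present definition. If the investigators want the intraoperative picture, treated intraoperative hypotension can be a separate descriptive item taken from the anesthesia record for both arms, not merged into the Aim 4 hypotension component. State which event set the Aim 4 comparison uses.

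The cost is a short amendment and a few CRF fields. No additional patients or study procedures are needed.
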